Benefits of study participation: Benefits to subjects include the possibility that their depression improves with this intervention. There are theoretical grounds and other research evidence indicating that TBS has potential beneficial effects on depression and executive dysfunction. The side effect profile for TBS is predicated on the side effect profile of repetitive Transcranial Magnetic Stimulation (rTMS). TMS was cleared as a depression treatment by the FDA in 2008. According to [name] clinical experience (Director of the TMS clinic at Washington University), patients often seek alternative treatments to medications, because medications have the potential for systemic side effects. TMS is generally an amenable treatment to patients.

Benefits to society: Depression in older adults with co-existing executive function impairment has devastating consequences including a protracted and treatment resistant depression course, poor quality of life and increased risk for suicide. Testing TBS intervention will inform research in this area of significant public health relevance.

2.f Early Withdrawal of Subjects

Subjects can terminate their participation at any time.

Subjects will be terminated by the PI if they experience a new event that will compromise their safety to receive the study intervention. For example, subject becomes sick and

her/his new condition precludes the use of the study intervention. Or, subject experiences a seizure during the intervention administration; this will preclude further study intervention sessions. Subjects can be withdrawn due to other medical or psychiatric events that in the judgment of the PI will compromise subject's safety to receive iTBS.

In addition, subjects may be terminated due to missing sessions. More than four consecutive missed sessions will cause withdrawal from study. Missed sessions will have to be made up, in this way the subject will still receive the entire 20-30 interventions, but over a longer time period (i.e. greater than 4-6 weeks). Missing more than six non-consecutive sessions (20% of the intervention), which cannot be made up will also lead to study withdrawal.

All missed intervention days will be recorded in a log for each participant.

2.g When and How to Withdraw Subjects

Subjects can withdraw their consent to participate at any time. Subjects should inform the study team about their wish to withdraw or sent a withdrawal letter.

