Subject's termination from study by PI will be documented in Case report forms.

2.h Data Collection and Follow-up for Withdrawn Subjects

All data collected from subjects up to their withdrawal date will be used for analysis.

If a subject decides to withdraw, we will ask him/ her to come for a close out visit to complete the same mood and executive function assessments that were recorded at baseline.

D3 Study Device: rTMS device

3.a Description of the rTMS device used to deliver iTBS vs sham (placebo)

We will use the rTMS device currently available at our institution for clinical and research applications. The stimulator is a MagPro R 30 magnetic stimulator manufactured by MagVenture A/S (Farum, Denmark) and FDA approved for treatment of major depressive disorder. Equipment components include: 1) R30 magnetic stimulator 2) coil cooler unit 3) dedicated C-B60 butterfly coil for Motor threshold assessments only 4) Treatment chair with neck rest and cloth cover, subjects will recline in this comfortable motorized recliner during intervention delivery 5) Head Stabilizer System (Airtight Pillow and Evacuation Pump).

The intervention will be delivered using:

- A Coil- cool B65 A/P butterfly coil. This coil functions as both active and sham coil. The coil has a symmetrical design, one side of the coil delivers active treatment and the other side delivers sham. Both sides of the coil are identical.
- Theta burst delivery software
Maglink software, this software interfaces with the B65 A/P coil to deliver the randomization assignment. The software provides codes assignments according to the randomization schedule to ensure double -blind conditions

The Magpro R30 is a non-significant risk device because:

- It is not an implant
- It is not for use in supporting or sustaining human life
- It does not present a potential for serious risk to the health, safety or welfare of study

3b. Other devices used:

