A randomization scheme generated by the study statistician will be used. Subjects who consent to study participation will be randomized to receive six weeks of either iTBS or sham. Each subject enrolled in the study will have equal probability to be randomized in each study arm and permuted blocks of randomly varying sizes (4, 6, and 8) will be used to generate the scheme. Each block will contain equal numbers of assignments to iTBS and sham providing a balanced design. Neuropsychological testing, mood assessments and fMRI scans will be performed pre- and post-intervention.

3.d Subject Compliance Monitoring

Subjects will receive a total of 30 study intervention sessions, administered once daily, Monday thru Friday for six weeks. Single- day intervention sessions missed due to expected (holidays) or unexpected (eg. Inclement weather, illness, transportation difficulties) reasons will have to be made up, in this way the subject will still receive the entire 30 interventions, but over a longer time period (i.e. greater than 4-6 weeks). More than four consecutive missed sessions will cause withdrawal from study. Missing more than six non-consecutive sessions (20% of the interventions), which cannot be made up will also lead to study withdrawal.

All missed intervention days will be recorded in a log for each participant, and reviewed (weekly if no adherence is detected, so that study staff can intervene) by the PI.

3.e Prior and Concomitant Therapy

Subjects may continue existing antidepressant treatments (which are not part of excluded medications). However, subjects will be asked not to make changes on antidepressant doses in order to maintain a consistent regimen of medications during TBS intervention. Likewise, if a subject is receiving psychotherapy, this regimen should not be modified.

E Study Procedures

E1 Screening for Eligibility

A phone screen will be performed prior to the first study visit. Over the phone the participant will be given a detailed description of the study including risk/benefits. They will be asked to provide information to help determine eligibility. Questions include demographics and health questions related to subject's history of depression,

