- Intervention will be delivered in a suite equipped with necessary materials to assist the subject in case of a seizure (oxygen, pulsoxymetry monitor, etc.).

Besides the suite is located in house Barnes Jewish hospital and the emergency response team at Barnes Jewish hospital is readily available to assist. The TMS treater will call the emergency response team in case of a seizure or other event deemed an emergency.

- The TMS suite has a written protocol to handle a seizure occurrence
- Subjects with increased risk of seizure or history of head trauma that may increase seizure won't be eligible for intervention. Besides we will screen subjects with The TMS

Adult Safety Screen (TASS) prior to iTBS intervention.

- Cognitive function is monitored throughout the intervention.
- Side effects of the intervention will be monitored weekly with the Frequency, Intensity and Burden of Side Effects rating (FIBSER). If deemed clinically necessary side effects will be also monitored by the study physician. Besides, subjects will be asked about side effects and will be monitored on all intervention days by the staff member administering the interventions.
- Hearing will be protected by the use of earplugs during intervention sessions

Interventions to minimize risk of worsening of mood and suicide risk:

- Depressive symptoms will be monitored weekly and every day subjects will be asked about how is their mood. Standardized mood scales are administered pre and post intervention.
- Emergent suicidal ideation will be monitored daily during the intervention and suicidal ideation will be assessed weekly with the 21-item Scale for Suicidal Ideation SSI,
- During the course of the intervention if necessary, [name] will perform a safety assessment. If clinically indicated, severely depressed patients will be advised hospitalization for close monitoring of their depressive symptoms. Hospitalization will be reported as a serious adverse event and the participant will be terminated from the study protocol.

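### Section D2 2.h requests the second MRI from no early leaver and leaves unclear whether subjects terminated by the PI are asked for any end assessment, although the analysis is stated as intention to treat

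*Combined protocol and SAP*

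**What the plan says.** Section D2 2.h covers follow-up of withdrawn subjects. It states that "All data collected from subjects up to their withdrawal date will be used for analysis", and then: "If a subject decides to withdraw, we will ask him/ her to come for a close out visit". The visit repeats the baseline mood and executive function assessments; imaging is not mentioned. For the other way of leaving, section 2.g says that a subject's "termination from study by PI will be documented in Case report forms" and adds nothing on assessment.

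Several rules can end a subject's participation without the subject choosing it:

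- Section 2.f: "Subjects can be withdrawn due to other medical or psychiatric events that in the judgment of the PI" would make it unsafe to receive iTBS.
- Sections 2.f and D3 3.d: "More than four consecutive missed sessions will cause withdrawal from study".
- Section D3 3.d: "Missing more than six non-consecutive sessions (20% of the interventions), which cannot be made up will also lead to study withdrawal".
- Section E3: if clinically indicated, "severely depressed patients will be advised hospitalization for close monitoring of their depressive symptoms", and "Hospitalization will be reported as a serious adverse event and the participant will be terminated from the study protocol".

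Section E2 schedules MADRS at weeks 2, 4 and 6. After baseline, the Toolbox battery is given once, at the end of the intervention, and the MRI is repeated once, at a post-intervention visit. Section F states intention to treat, a t-test on changes and a mixed model with a time-by-group term. It gives no method for missing outcomes. It also says the pilot data will be used to size a later trial.

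**The concern.** An intention-to-treat comparison needs outcomes from randomised subjects whether or not they finish treatment. Here the written request for end data is tied to a subject's own decision to leave, and the scan is left out of it. At least one route to termination is linked by the protocol itself to the mood outcome: hospitalisation is to be advised for severe depression, and hospitalisation ends participation.

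The exposure differs by outcome. A subject without the single post-baseline Toolbox value or scan contributes nothing to the estimate of change on that measure, whatever model is fitted. MADRS is better protected, because weeks 2 and 4 are collected and 2.h keeps data up to withdrawal. That protection works only if those visits enter the model, and section F describes the model as baseline to post-intervention without naming them.

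If outcome-related losses differ between arms, the Toolbox contrast (Aim 1) and the connectivity contrast (Aim 2) are shifted, as are the effect estimates carried into the next trial's sample size.

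**Working it through.** **1. Who is asked for what.** Setting 2.g, 2.h and E2 side by side:

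| Subject | End MADRS | End Toolbox executive tests | Second MRI |
|---|---|---|---|
| Completes | week 6 | once, end of intervention | once |
| Decides to withdraw | requested | requested, but tests not named | not requested |
| Terminated by PI | not stated | not stated | not stated |

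The MRI gap holds on any reading of 2.h. The Toolbox gap depends on whether 2.h is meant to include PI-terminated subjects. Two smaller ambiguities follow. First, E2 lists the Toolbox executive tests at the screening visit, not the baseline assessment visit, so a reference to what was recorded at baseline does not clearly name them. Second, keeping data up to the withdrawal date does not say whether close-out values taken after that date count.

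**2. Plan figures.** There is no power calculation to reproduce; 20 subjects rests on feasibility. The simple sums agree: 10 + 10 = 20 subjects, and 6/30 sessions = 20%.

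**3. Size of a possible shift.** The documents give 10 per arm and a two-sided alpha of 0.05. They give no SD or drop-out rate, so the number lost and the gap below are assumptions. If k of 10 subjects in one arm have no end value and differ from those retained by a gap D (in SD of change), the retained mean departs from the full-arm mean by (k/10) × D.

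- k = 1, D = 0.5: 0.1 × 0.5 = 0.05 SD
- k = 1, D = 1.0: 0.1 × 1.0 = 0.10 SD
- k = 1, D = 1.5: 0.1 × 1.5 = 0.15 SD
- The same k and D in both arms: the two shifts subtract to 0.

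**4. Against sampling error.** At 9 versus 10, SE = sqrt(1/9 + 1/10) = 0.459 SD. The shift is then 0.05/0.459 = 0.11 SE to 0.15/0.459 = 0.33 SE. With no true effect, the noncentral t distribution gives two-sided rejection of 5.1%, 5.5% and 6.1% for shifts of 0.05, 0.10 and 0.15 SD, against the nominal 5%.

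**5. An extreme case for one loss.** Suppose the single worst of 10 subjects is always the one lost, in one arm only. The expected gap is 1.71 SD, so the shift is 0.1 × 1.71 = 0.17 SD. A simulation with 100,000 replicates gave a bias of 0.17 SD and rejection of 7.5%. That rate is higher than the shift alone implies, because removing an extreme value also shrinks the observed variance.

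**The case against.** A reader might infer that 2.h reserves the close-out visit for voluntary withdrawers and shuts out everyone the PI terminates. The text does not go that far. It does not restrict the visit in those terms and does not forbid assessing others. The heading of 2.h refers to withdrawn subjects generally, and 2.f uses the language of withdrawal for PI decisions too. What stands is an ambiguity for PI-terminated subjects and a plain omission for MRI.

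The outcome-related route is also narrow. The safety wording in 2.f concerns fitness to receive the intervention. Missed sessions are to be made up, and the six-session limit counts only those that cannot be. Subjects unsafe for outpatient care are excluded at entry. That leaves mainly hospitalisation for severe depression. The documents give no reason to expect a particular number of such losses, or more of them in one arm.

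Finally, the trial is a 20-subject pilot sized on feasibility, and one lost subject moves the contrast by a fraction of a standard error. This stands, and it limits severity. It does not remove the case for the change, because an assessment not requested when a subject stops may not be recoverable later.

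**Conclusion.** The point holds as a minor, cheap improvement. As written, no early leaver is asked for the second scan, and PI-terminated subjects are not clearly asked for the single post-baseline Toolbox value. Both sit badly with the stated intention to treat.

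A reader might go on to conclude that the Toolbox or fMRI results will be materially biased. The documents do not support that. The shift of 0.05 to 0.15 SD rests on an assumed single loss in one arm and an assumed gap of 0.5 to 1.5 SD. Even the extreme single loss gives about 0.17 SD and 7.5% rejection, and equal losses and gaps in both arms give none. More than one loss would scale the shift in proportion, but nothing in the documents says how many to expect. The case for acting is consistency with the analysis principle at low cost.

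**What to change.** In section D2 2.h:

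- Keep the present close-out request for subjects who decide to withdraw, and extend it to every randomised subject who stops early for any reason, including termination by the PI, if the subject agrees.
- Name MADRS and the three Toolbox executive tests (Flanker, Dimensional Change Card Sort, List Sorting). Add the already planned post-intervention MRI where the MRI screen in E3 and the investigator's judgment allow.
- State the timing: at the planned 6-week point where possible, otherwise at discontinuation, with the date recorded.
- State that these values are analysed in the randomised arm, and that close-out values collected after the withdrawal date are included.

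Reconcile this with the termination wording in E3 and the withdrawal wording in 2.f and D3 3.d, so that leaving the intervention does not by itself end data collection. The clinical stopping rules remain with the sponsor.

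In section F, state that the MADRS mixed model uses weeks 2, 4 and 6. Add one simple sensitivity range for missing Toolbox and fMRI values, with lost subjects taken as 0 to 1.5 SD worse than retained subjects in the same arm.

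The cost is one paragraph in 2.h, a few sentences in section F and matching wording elsewhere, plus a few extra visits and scans of about 60 minutes among 20 subjects. Some end values will be taken after partial treatment, which is why the date should be recorded.

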Brain's connectivity measure: Resting State Functional Connectivity (rsFC) is based on the principle that functionally related brain regions exhibit correlated activity in intrinsic very low frequency (~ 0.1 Hz) Blood Oxygen Level Dependent (BOLD) signal. Such low-frequency BOLD fluctuations constitute an indirect measure of spontaneous neural activity. This approach has identified canonical resting state networks, defined as neural systems exhibiting intrinsic brain activity which is temporarily correlated with widely distributed brain regions. Using resting state fMRI we will measure functional connectivity within the Cognitive Control Network (CCN) in depressed older adults before and after study intervention. We will also explore functional connectivity within and between other networks that are relevant to depression including the Default Mode network and the cingulo-opercular networks.

D Study Design

D1 Overview or Design Summary

[figure not shown]

Figure 1. Study Design: Subjects will receive a total of 30 session of intervention (daily Monday – Friday) for 6 weeks. Executive function and mood assessments will be performed pre- and post-intervention.

D2 Subject Selection and Withdrawal

2.a Inclusion Criteria :

- 1) Age \geq 60 – 85 years old
- 2) Diagnosis of major depressive disorder (MDD), single or recurrent, with a current Major depression episode as diagnosed by the Mini-international Neuropsychiatric Interview (MINI 6.0)
- 3) Montgomery Asberg Depression Scale score greater than or equal to 15 at baseline.
- 4) Evidence of decreased executive function as evidenced by either of the following conditions: a) scoring below the mean normative scaled score on the average of the NIH Toolbox executive function measures: Flanker inhibitory control and attention test and the Dimensional sort card test, approximate score 70 – 100 as per PI discretion. b) Discrepancy of at least 10 points between the average of the picture vocabulary score and the reading recognition test score and the average of the Flanker inhibitory control and dimensional card sort test score. c) Frontal Systems Behavior Scale (FRSBE) T scores above 60 (indicative of borderline to clinically significant impairment) and at least 10 points (1 Standard Deviation) above subject's premorbid (pre-depression) scores.

Exclusion Criteria

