Motor Threshold Determination: Each subject's Motor Threshold (MT) will be assessed using a dedicated C-B60 butterfly coil before the first intervention session. The MT will be re-assessed at the beginning of intervention weeks 2, 4 and 6 and re-checked as needed according to PI instructions, for example if the subject has had any medication changes or other conditions that may cause fluctuations in the MT. MT is the lowest stimulation intensity required to induce a motor response of the Abductor Pollicis Brevis (APB) muscle in the contralateral hand. MT will be measured via the visualization method, by observing movement of the contralateral thumb or adjacent fingers. Because of our subjects' age range, we will "dose" iTBS at 120% of the resting MT. This dosing is necessary to adjust for prefrontal atrophy in the elderly. This dosing has been used in a large sample without serious adverse events.

In order to ease subjects into stimulation we will begin the first intervention at the level of MT and titrate up to 120% of the MT during the first week of intervention. Subjects will achieve 120% of MT by the end of the first week.

The TMS device to be used in this study for delivery of the interventions is currently employed in clinical operations and is housed at the West Pavilion, suite 15340, Outpatient Psychiatric Clinic at [name]. The equipment will remain in place once study is finished. Therefore, there is not need for maintaining device shipment and receipt records.

The equipment used for neuronavigation procedures is located at the Laboratory for Applied Brain Plasticity (LABP) on the East Building located at [name] and it is currently used in research operations.

Scanning facilities :

Scanning facilities: MRI scans will be performed at the following scanning facilities at Washington University:

- Center for Clinical Imaging Research (CCIR): The CCIR is located on the 10th floor of Barnes-Jewish Hospital West Pavilion. The CCIR possesses four dedicated research scanners, which include a 3T MRI Siemens scanner which will undergo PrismaFit upgrade.
- The MRI facility at the Mallinckrodt Institute of Radiology: located at [name]. This facility houses 2 PRISMA 3T Systems.

3.c Method for Assigning Subjects to Intervention Groups

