medications. Other questions include those to rule out contraindications to TMS such as metal in the head, a personal history of seizures or severe head trauma. Questions about contraindications to MRI will be asked as well. If participant meets eligibility criteria based on that information an appointment will be scheduled to review and discuss the informed consent in person.

E2 Schedule of Measurements

After providing informed consent the following procedures will begin.

Screening visit (Visit 0)

At this visit a psychiatric interview will be performed by PI or her designee, during the visit the diagnosis of major depressive disorder will be confirmed, and information about subject's health status and ongoing medications will be obtained. Also a safety assessment will be performed to rule out the presence of active suicidal ideation with plan and imminent danger which will preclude study participation.

Screening assessments include:

Montreal Cognitive Assessment (MoCA)

TMS Adult Safety Screen (TASS)

MINI

FrSBE

Montgomery Asberg Depression Rating Scale (MADRS) (Repeat it at Baseline Assessment Visit if screening visit is done more than a week prior to intervention)

National Institute of Mental Health Tool Box will be administered using an IPAD application. The tests include:

NIH Toolbox Picture Vocabulary Test (TPVT)

NIH Toolbox Flanker Inhibitory Control and Attention Test (Flanker)

NIH Toolbox Dimensional Change Card Sort Test (DCCS)

NIH Toolbox Picture Sequence Memory Test (PSMT)

NIH Toolbox List Sorting Working Memory Test (List Sorting)

NIH Toolbox Pattern Comparison Processing Speed Test (Pattern Comparison)

NIH Toolbox Oral Reading Recognition Test (Reading)

NIH Toolbox Oral Symbol Digit Test

NIH Toolbox General Life Satisfaction

Screen visit will take about 145 minutes to complete.

If subject qualifies for the study a baseline visit will be conducted.

Baseline Assessment Visit

At this visit the following assessments will be administered:

Trail Making Test

Semantic Fluency Test

The Revised Observed Tasks of Daily Living (OTDL-R)

Delis-Kaplan Executive Function System (D-KEFS): Color-word interference

Quick Inventory of Depressive Symptoms Self report

Anxiety Measure (self report)

Ruminative Response Scale (RRS) (self report)
NIH Toolbox – General Life Satisfaction CAT and Positive Affect CAT
Cumulative Illness Rating Scale-Geriatric (CIRS-G)
The Antidepressant Treatment History Form (ATHF)

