Subjects assigned to iTBS: Burst of three stimuli at 50 Hz, repeated every 200ms using a two-seconds train repeated every 10 seconds for a total of 190s (600 pulses). TBS will be delivered over the scalp over the brain area corresponding to the dorsolateral prefrontal cortex. We will apply stimulation bilaterally with a total of 600 pulses on the left and 600 pulses on the right. This protocol takes about 8 minutes to complete.

Subjects assigned to Sham: Stimulation will be delivered mimicking the pulse

frequency, sound and sensation of the active stimulation but with not active magnetic pulse delivery.

Intervention delivery # 2- 30: Subsequent interventions will be scheduled daily Monday to Friday the theta burst stimulation paradigm as described above will be used.

Weekly assessments:

We will obtain the following assessments on a weekly basis, at the end of the intervention week.

Montgomery Asberg Depression Rating Scale (Week 2, Week 4, and Week 6 only*)

Quick Inventory of Depressive Symptoms Self report

21 item for suicidal ideation (SSI)

Frequency Intensity and Burden of side effects (FIBSER)

Altman Self Rating Mania Scale (ASRM)

NIH Toolbox – General Life Satisfaction CAT and Positive Affect CAT (Baseline, Week 2, Week 4, and Week 6 only*)

Anxiety Measure (self-report) (Baseline, Week 2, Week 4, and Week 6 only*)

Ruminative Response Scale (RRS) (self report) (Baseline, Week 2, Week 4, and Week 6 only*)

End of intervention assessments:

At the end of 6 weeks, or 30 interventions we will repeat the NIH Tool box battery, Semantic Fluency, Trail Making Test, FrSBE, the Revised Observed Tasks of Daily Living (OTDL-R), Delis-Kaplan Executive Function System (D-KEFS): Color-word interference, the California Verbal Learning Test – second edition (CVLT-II), and the Line Orientation test from RBANS in addition to the weekly assessments. This assessment session will take about three hours to complete.

Post-intervention MRI Scan Visit

Neuroimaging Pre-Scan Questionnaire

Post-intervention MRI scan (about 60 minutes)

This visit will take one hour and half to complete.

E3 Safety and Adverse Events

Interventions and precautions to minimize subject's risk during TBS intervention:

- Treating personnel is trained to act as first line responder, and will have cardiopulmonary resuscitation (CPR) training, in case of a seizure event.

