Statistical Analyses: We will use intention-to-treat principles. We will use t-test or its non-parametric equivalent to compare the distribution of continuous variables and the changes in the main outcome measures between active and sham groups. χ^2 tests will be used to compare categorical variables between groups. We will use a mixed general linear model (GLM) to accommodate data from our within- and between-participant study design to examine changes from baseline to post-intervention, and compare them between active vs. sham groups. The GLM explores estimated marginal means by taking into account within- and between-participant variability, adjusting for confounders and allowing exploration of significance of within-participant and between-group interaction effects. Differences between groups in behavioral outcome measures and network connection changes will be evaluated through 2-way interaction effect (time*group). Through the 2-way interaction iTBS*Fazekas score we will explore the modification effect of grade of white matter burden on the impact of iTBS in the observed network connectivity changes. Pearson's correlation will examine the correlation between changes in behavioral measures with changes in network connectivity. We will use Hayes' PROCESS¹¹⁴ macro to evaluate the role of the difference in the strength of connections pre-intervention minus the strength of connection post intervention as mediator of change for iTBS and bootstrap and Monte Carlo confidence intervals will be calculated. All statistical tests will be two-sided and evaluated at the alpha level of 0.05. SAS 9.4 (SAS Institute, Cary, NC) and R 3.2.3 statistical software packages will be used for all analyses. Sample size justification: For this pilot study, I plan to enroll 20 elderly subjects and randomized them to iTBS arm or placebo arm (10 in each group). The sample size of 20 subjects is feasible for the time limit of the KL2 award. This pilot sample will provide meaningful data to estimate sample size and calculate power for a subsequent grant application to rigorously test the effects of theta burst stimulation on depressed older adults.

G Data Handling and Record Keeping Records retention:

Study data will be kept for potential future analysis. Records will be maintained for at least 7 years after completion of the study as per local HRPO requirements.

G1 Confidentiality and Security

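### Section F tests the arm effect on change without adjusting for the outcome's baseline value; a baseline-adjusted main analysis costs little and may gain precision

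*Combined protocol and SAP*

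**What the plan says.** Section F names two routes to the arm comparison. The first is a t-test or its non-parametric counterpart on "the changes in the main outcome measures between active and sham groups". The second is a mixed general linear model of baseline and post-intervention data, in which group differences "will be evaluated through 2-way interaction effect (time*group"). The model is described as "adjusting for confounders and allowing exploration of significance", but no confounder is listed, the baseline score is not named as a covariate, and neither route is called the main one.

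The data for adjustment exist. Section 2.d says that neuropsychological tests, mood ratings and scans are done before and after the intervention. E2 schedules "Montgomery Asberg Depression Rating Scale (Week 2, Week 4, and Week 6 only"). Section 2.h commits to using all data up to withdrawal and asks withdrawing subjects to attend a close-out visit with the baseline mood and executive assessments. Section F states intention-to-treat principles.

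Two details bear on the size of any gain and on what baseline means. Some outcomes are also entry criteria in 2.a: "Montgomery Asberg Depression Scale score greater than or equal to 15 at baseline", and, as one of several alternative conditions, "scoring below the mean normative scaled score on the average of the NIH Toolbox executive function measures" (Flanker and card sort). For MADRS at screening, E2 adds: "Repeat it at Baseline Assessment Visit if screening visit is done more than a week prior to intervention". Some subjects may therefore have two pre-treatment scores.

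**The concern.** In a randomised trial with a baseline for each outcome, the change score fixes the weight on baseline at one. ANCOVA estimates that weight from the data and so removes the part of chance baseline imbalance that the change score handles badly. With 10 per arm such imbalance can be large. The trial's stated use is to supply estimates for sizing a later trial, so the width of its intervals matters more than its p-values. At stake is precision that could be had from data already collected. The validity of the planned tests is not in question.

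**Working it through.** **Inputs from the documents.** Section F gives N = 20, 10 per arm, two-sided alpha 0.05. The only arithmetic behind N is 10 + 10 = 20. It rests on feasibility, with no effect size, SD or power, so there is no power figure to reproduce.

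**Assumed inputs.** Baseline-post correlation ρ of 0.3, 0.5 and 0.7; ratio k of baseline SD to post SD; a true effect of 0.8 post-score SD for power.

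**Step 1: do the two planned routes differ?** With complete pre/post data the time-by-group coefficient is the difference in mean change. In one simulated 20-subject data set, the t-test on change gave −1.457 (t = −2.567) and the random-intercept model gave −1.457 (t = −2.567). ANCOVA on the same data gave −1.485 (t = −3.645). So the mixed model does not itself supply baseline adjustment. One data set shows that the estimators differ, not how large the gain is.

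**Step 2: variance with equal SDs (k = 1).** In units of the post variance times 2/n:

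- change score: 2(1 − ρ)
- ANCOVA: (1 − ρ²) × (2n − 3)/(2n − 4) = (1 − ρ²) × 17/16 at n = 10
- ratio: (1 + ρ)/2 × 17/16

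| ρ | Ratio ANCOVA/change | Power, change | Power, ANCOVA |
|---|---|---|---|
| 0.3 | 0.65 × 1.0625 = 0.69 | 30% | 40% |
| 0.5 | 0.75 × 1.0625 = 0.80 | 40% | 47% |
| 0.7 | 0.85 × 1.0625 = 0.90 | 59% | 63% |

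Power is from the noncentral t with 18 and 17 degrees of freedom. For example, at ρ = 0.5 the standard errors are √1 × √0.2 = 0.447 and √0.75 × √0.2 × √1.0625 = 0.399, so the noncentrality rises from 1.79 to 2.00. Simulation (20,000 trials per ρ) gave ratios of 0.69, 0.80 and 0.89, with type I error between 4.9% and 5.2% for both methods at these ρ.

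**Step 3: where the gain ends.** Setting (1 + ρ)/2 = 16/17 gives ρ = 32/17 − 1 = 0.88.

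**Step 4: narrowed baseline spread.** In general the ratio is (1 − ρ²)(17/16)/(1 + k² − 2kρ).

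- k = 0.8: 0.83, 0.95, 1.04 at ρ = 0.3, 0.5, 0.7.
- k = 0.6: 0.97, 1.05, 1.04.
- Baseline truncated at its mean (ρ before truncation; simulated, 40,000 trials): 0.89, 0.95, 1.00.

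Across the last two, stronger scenarios the range is about 0.89 to 1.05, and power at 0.8 SD moves by between +4 points (37% to 41%) and −2 points (49% to 47%).

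**Step 5: the worst case.** Since 1 + k² − 2kρ = (1 − ρ²) + (k − ρ)², the denominator is smallest at k = ρ. The ratio there is 17/16 = 1.0625, a loss of about 6%. This covers baseline spreads no larger than the post spread, which is the case that entry cut-offs create.

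**The case against.** The strongest reply is that this is a preference. Both planned methods are valid under 1:1 randomisation, the study is a feasibility-sized pilot, and ANCOVA does not rescue power: at ρ = 0.5 it still has only about 47% for the assumed effect. All of that stands, and it is why the point is graded as an improvement.

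A second reply is that the gain is not assured. MADRS, and in part Flanker and card sort, are used for entry, and a very stable test score could have ρ near 0.88. This also stands. List Sorting and connectivity have no direct cut-off in 2.a.

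A third is that a plain week-6 ANCOVA of MADRS would drop subjects without a week-6 value, against 2.h and the intention-to-treat commitment. This is correct and shapes the fix.

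It might also be said that the unnamed confounders could include baseline. Even so, subject-level covariates entered only as main effects do not change the time-by-group estimate when data are complete. A fitted example gave −0.2638 with and without the covariate.

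That same fact rules out a stronger reading. A reader might infer that choosing covariates after seeing the data inflates type I error, to about 8% with any subset of three unrelated covariates, or 12% to 13% if baseline adjustment is also optional. Those simulated figures take the smallest p-value and assume covariate-by-time terms or regression of change on the covariates. Section F mentions neither. Some software adds such terms by default, and incomplete data would break the invariance, so the risk is not nil, but the documents do not support those figures.

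**Conclusion.** The point holds as a cheap improvement to a valid plan. Neither planned comparison adjusts for the outcome's baseline. Under assumed correlations of 0.3 to 0.7 with equal SDs, adjustment would cut variance by 31% to 10%. The benefit vanishes at a correlation of about 0.88 and could be nil or slightly negative for outcomes whose baseline spread is narrowed by the entry criteria. The documents give no correlation, SD or effect size, so no single figure can be claimed. A reader might infer that the planned tests are biased or that adjustment guarantees more power; neither follows. The missing ranking of the two routes, the unnamed confounders and the undefined MADRS baseline are gaps in detail that the same edit would close.

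**What to change.** In Section F, make the main between-arm analysis baseline-adjusted:

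- **MADRS:** a repeated-measures model of weeks 2, 4 and 6 with arm, visit, arm-by-visit and baseline MADRS as covariate, reporting the week-6 arm contrast. Subjects who withdraw then contribute the visits they completed.
- **Each NIH Toolbox executive measure and CCN connectivity:** an ANCOVA of the post-intervention value on arm and the baseline value, including close-out assessments where obtained. Connectivity is listed in E4 under the primary outcome measures but falls under Secondary Aims in C2; its status should be stated.
- **Baseline:** the last value before the first session. For MADRS this is the repeat where there is one; for the Toolbox executive tests it is the screening value.
- **Sensitivity analysis:** keep the t-test or rank test on change.
- **Covariates:** replace the reference to confounders with the baseline value and any other covariate named in advance. Keep the list short: a second covariate unrelated to the outcome multiplies variance by (1 + 2/15)/(1 + 1/16) = 1.067, about 7%.

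The cost is a few sentences. No new data are needed, and the SAS and R packages already named fit both models. The statistical price of the baseline term is one degree of freedom and at most about 6% in variance when baseline spread is no larger than post spread.
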